#### **7.1.1.3 Baseline Visit (Visit 0)**

Once the screening central clinical laboratory tests and 12-lead ECG results have been obtained, in addition to repeat assessments (if required), and the subject has completed the required washout period (if applicable), the subject will return to the site for the baseline visit (Visit 0).

Inclusion/exclusion criteria must also be reviewed during this visit to ensure subjects continue to meet all eligibility criteria.

Table 1 outlines all procedures to be conducted during the baseline visit (Visit 0) with further clarification provided below:

- For subjects with more than 30 days since the safety measurements at the screening visit (Visit -1) were collected, an abbreviated physical examination, clinical laboratory tests, and 12-lead ECG must be repeated, and the results reviewed by the investigator prior to the subject being enrolled.
- After 5 minutes rest, blood pressure, and pulse will be collected 3 times (with at least 2 minutes in between each collection) during the visit. The average of each set of 3 measurements will be used to determine continued participation in the study (see Section 4.4.1).
- Three ECGs will be taken, with approximately 5 minutes in between each one, to ensure appropriate baseline intervals are established. The investigator will perform the initial interpretation of the ECG immediately after collection to ensure the safety of each subject to continue with the study. The ECG tracing will be sent to the central reader for analysis. Upon review of the report from the central reader, the investigator will re-evaluate the clinical significance of the ECG in light of other safety data for the subject. If abnormal and significant results are observed following assessment by the central reader, the investigator, in consultation with the appointed CRO medical monitor, will confirm the subject's continued participation in this study.
- The C-SSRS "Since Last Visit" Version of the Pediatric/Cognitively Impaired Version should be completed.
- For eligible subjects, the investigator or assigned site staff designee will access the IWRS to enroll the subject and obtain an investigational product bottle number to dispense to the subject. Subjects will be dispensed a bottle of investigational product to cover them until their next regularly scheduled visit. Subjects will be instructed to take 1 capsule each day. Dosing will begin the morning following the baseline visit (Visit 0).

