#### **7.2.4.8 Children's Sleep Habits Questionnaire and Sleep Diary**

The Children's Sleep Habits Questionnaire (CSHQ) is a parent report questionnaire designed to screen for the most common sleep problems in children, and consists of 33 items for scoring and several extra items intended to provide administrators with other potentially useful information about respondents. The instrument evaluates the child's sleep based on behavior within 8 different subscales: bedtime resistance, sleep-onset delay, sleep duration, sleep anxiety, night wakings, parasomnias, sleep-disordered breathing, and daytime sleepiness. The CSHQ will be conducted at each visit to the site starting with the baseline visit (Visit 0) and will be completed by the subject's parent(s)/LAR.

The subject's parent(s)/LAR will complete a sleep diary to log daytime napping, bedtime, and wake time.

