## 9.9 Safety Analyses

The Safety Analysis Set based on either the interim analysis dataset or all cumulative data up to study completion, whenever it is appropriate, will be used to report the safety data.

Clinical laboratory tests, vital signs, and ECG findings will be summarized by treatment group and visit using appropriate descriptive statistics. Potentially clinically important findings will also be summarized by treatment group and listed.

Adverse events will be coded using the Medical Dictionary for Regulatory Activities. TEAEs are defined as AEs that start or deteriorate on or after the date of the first dose of investigational product and no later than 3 days following the last dose of investigational product in the double-blind phase.

Treatment-emergent AEs will be summarized. The number and percent of subjects with TEAEs will be calculated for each system organ class, by preferred term, and by treatment. The severity of the TEAEs, the relationship to the investigational product, TEAEs causing study discontinuation, serious AEs and death will also be presented.

The CSHQ will be summarized by treatment group using appropriate descriptive statistics at each visit.

Sleep diary data will be descriptively summarized by treatment group.

A summary and listing of the C-SSRS data will be provided for subjects with a positive response only.

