11. SAFETY ANALYSES

The Safety Analysis Set based on either the interim analysis dataset that for the safety summary at interim analysis, or the interim analysis dataset together with the overrun if the efficacy criterion meets, or all cumulative data up to study completion, whenever it is appropriate, will be used to report the safety data.

Safety data will be summarized by SPD489 dose strengths, pooled doses and placebo. Safety variables include AEs, clinical laboratory variables, vital signs, physical examinations, Children's Sleep Habits Questionnaire (CSHQ), sleep diary, ECG, and C-SSRS variables. For each safety variable, the last value collected before the first dose of investigational product will be used as baseline for all analyses of that safety variable.

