Descriptive statistics (n, mean, SD, minimum, median, and maximum) for ECG variables (heart rate, PR interval, RR interval, QRS interval, QT interval, and QTc interval) and their changes from baseline at each assessment time point will be presented by treatment group. QTc interval will be calculated using both Bazett ($QTcB = QT/(RR)^{1/2}$) and Fridericia ($QTcF = QT/(RR)^{1/3}$) corrections; if RR is not available, it will be replaced with 60/hr in the correction formula. ECG interpretation will be summarized by visit (and Visit 6/ET) and treatment group. A shift table from baseline to each visit (and Visit 6/ET) for qualitative ECG results will also be presented.

All ECG values will be listed for the Safety Analysis Set.

Electrocardiogram variable values, include unscheduled visit, will be considered PCI if they meet either the observed value criteria or the change from baseline criteria listed in [Table 4](#). The number and percentage of subjects with post-baseline PCI values will be tabulated by treatment group. The percentages for the observed value criteria will be calculated relative to the number of subjects with at least 1 post-baseline assessment available per parameter and visit. The percentages for the change from baseline criteria will be calculated relative to the number of subjects with available baseline and at least 1 post-baseline assessment per parameter and visit. The numerator is the total number of subjects with at least 1 PCI post-baseline ECG value. A listing of all subjects with post-baseline PCI value will be provided including the subject number, site, baseline, and post-baseline PCI values.

Table 4: Criteria for Potentially Clinically Important ECG Values

| ECG Parameter | Unit | Observed Value | | Change from Baseline | |
|---------------|--------------|----------------|--|----------------------|--------------|
| | | Lower Limit | Higher Limit | Lower Limit | Higher Limit |
| ECG Result | - | - | Abnormal (core lab) and clinically significant from investigator | - | - |
| Heart Rate | Beats/minute | <55 | >130 | Decrease >15 | Increase >15 |

Table 4: Criteria for Potentially Clinically Important ECG Values

| | | | | | |
|---------------|------|---|--|---|-----------------------------------|
| PR Interval | msec | - | ≥ 200 | - | - |
| QT Interval | msec | - | ≥ 440 | - | ≥ 30 and < 60 ≥ 60 |
| QTcF Interval | msec | - | ≥ 440 and < 480 ≥ 480 and < 500 ≥ 500 | - | ≥ 30 and < 60 ≥ 60 |

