11.5 Other Safety Variables**11.6 Children's Sleep Habits Questionnaire and Sleep Diary**

The CHSQ consists of 33 items for scoring and several extra items intended to provide administrators with other potentially useful information about respondents. The instrument evaluates the child's sleep based on behavior within 8 different subscales:

1. Bedtime resistance (sum of the responses for Goes to bed at same time, Falls asleep in own bed, Falls asleep in other's bed, Needs parent in room to sleep, Struggles at bedtime and Afraid of sleeping alone)
2. Sleep-onset delay (Falls asleep in 20 minutes item)
3. Sleep duration (sum of the responses for Sleeps too little, Sleeps the right amount and Sleeps same amount each day)
4. Sleep anxiety (sum of the responses for Needs parent in room to sleep, Afraid of sleeping in the dark, Afraid of sleeping alone and Trouble sleeping away)
5. Night wakings (sum of the responses for Moves to other's bed in night, Awakes once during night and Awakes more than once)
6. Parasomnias (sum of the responses for Wets the bed at night, Talks during sleep, Restless and moves a lot, Sleepwalks, Grinds teeth during sleep, Awakens screaming, sweating and Alarmed by scary dream)
7. Sleep-disordered breathing (sum of the responses for Snores loudly, Stops breathing and Snorts and gasps)
8. Daytime sleepiness (sum of the responses for Wakes by himself, Wakes up in negative mood, Others wake child, Hard time getting out of bed, Takes long time to be alert, Seems tired, Watching TV and Riding in car)

Each subscale and each individual item will be summarized using descriptive statistics (n, mean, SD, minimum, median, and maximum) at each visit (and Visit 8/ET) by treatment group. All CSHQ data will be listed for the Safety Analysis Set.

Sleep diary data will be summarized at each visit (and Visit 8/ET) for total daytime napping time, nighttime sleep time and time to fall asleep using descriptive statistics (n, mean, SD, minimum, median, and maximum) by treatment group. Sleep diary data are collected daily. The average daily value per visit and their change from baseline will be summarized by treatment group. Sleep diary data will also be listed for the Safety Analysis Set.

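### SAP 11 defines a pre-dose baseline for the CSHQ, but SAP 11.6 plans no change-from-baseline or baseline-adjusted summary of it

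*SAP*

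**What the plan says.** Protocol 7.2.4.8 and Table 1 schedule the CSHQ at Visit 0 and at every later site visit. Protocol 7.1.1.3 starts dosing on the morning after Visit 0. A pre-dose score is therefore scheduled for each randomised child.

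SAP 11 lists the CSHQ among the safety variables and states that "the last value collected before the first dose of investigational product will be used as baseline for all analyses of that safety variable".

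For the CSHQ itself, SAP 11.6 says: "Each subscale and each individual item will be summarized using descriptive statistics (n, mean, SD, minimum, median, and maximum) at each visit", by treatment group, with a full data listing. Protocol 9.9 is no more specific: "The CSHQ will be summarized by treatment group using appropriate descriptive statistics at each visit". Neither names a change from baseline.

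Other repeated safety measures are handled differently:

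- Vital signs (SAP 11.3) are summarised as values "and their changes from baseline at each assessment time point will be presented by treatment group". ECG variables (SAP 11.4) get the same treatment.
- Laboratory values (SAP 11.2) get change from baseline to Visit 6/ET.
- The sleep diary, in SAP 11.6 itself, gets it too: "The average daily value per visit and their change from baseline will be summarized by treatment group".

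SAP 11.6 also refers twice to a Visit 8/ET. The last treatment visit in the Schedule of Assessments is Visit 6/ET.

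**The concern.** Sleep assessment is part of the stated safety objective (Protocol 2.2.2, SAP 3.2), and Protocol 1.2.2 names insomnia among the most frequently reported adverse events. The natural question is how each child's sleep score moved from before treatment, and whether it moved more on drug than on placebo. The plan collects the data and defines the baseline, but tabulates neither quantity.

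The sleep diary does not fill the gap. Table 1 footnote l has diaries first dispensed at Visit 0, and dosing starts the next morning, so the diary holds at most about one pre-dose night. The CSHQ is the sleep instrument with a full pre-treatment assessment.

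Safety is reported by individual dose as well as pooled, so the arms are small enough for chance baseline differences to be noticeable.

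**Working it through.** **Arm sizes.** Protocol 9.6 plans 156 completers, 20% dropout and 5:5:5:5:6 allocation.

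- Randomised: 156 / (1 − 0.20) = 195, as stated.
- Per dose: 195 × 5/26 = 37.5. Placebo: 195 × 6/26 = 45. Pooled 10, 20 and 30 mg: 3 × 37.5 = 112.5.
- Planned completers: 30 per dose and 36 on placebo.

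The documents give no SD, correlation or precision figure for the CSHQ, so there is no plan figure to reproduce for it. Everything below is in SD units, and r is an assumption.

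**Chance difference at Visit 0.** SE = √(1/n_active + 1/n_placebo).

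- One dose against placebo: √(1/37.5 + 1/45) = 0.22 SD, a 95% range of ±0.43 SD.
- Pooled doses against placebo: √(1/112.5 + 1/45) = 0.18 SD, a 95% range of ±0.35 SD.

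**How much carries forward.** With equal variances, a Visit 0 gap g adds about r × g to the raw follow-up difference and (r − 1) × g to the difference in change scores. For g = 0.43 SD, the edge of the single-dose range:

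| Assumed r | Into raw difference | Into change-score difference |
|---|---|---|
| 0.3 | +0.13 SD | −0.30 SD |
| 0.5 | +0.21 SD | −0.21 SD |
| 0.8 | +0.34 SD | −0.09 SD |

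Change scores thus reverse an imbalance; they do not remove it. Regression on the Visit 0 score removes it in expectation at any r.

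**Precision relative to the raw difference.** The variance ratio is 2(1 − r) for change scores and 1 − r² for the baseline-adjusted difference.

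| Assumed r | Change score | Baseline-adjusted |
|---|---|---|
| 0.4 | 1.20 | 0.84 |
| 0.5 | 1.00 | 0.75 |
| 0.6 | 0.80 | 0.64 |
| 0.8 | 0.40 | 0.36 |

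Change scores are more precise than raw values only if r > 0.5. The adjusted difference is never less precise, apart from one degree of freedom.

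**What the planned table cannot give.** Var(change) = s₀² + s₆² − 2·r·s₀·s₆. The table supplies s₀ and s₆ but not r. With s₀ = s₆ = s, the SD of change is s·√(2(1 − r)): 1.10s at r = 0.4 and 0.63s at r = 0.8. The same table is compatible with both.

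**Who is in each row.** Under the planned dropout, the Visit 0 mean for a dose arm covers about 37.5 children and the Visit 6 mean about 30. Subtracting one from the other is not a within-child change. A row combining Visit 6 with early termination would bring back some of those who stopped, but SAP 11.6 attaches that row to a visit that does not exist.

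**The case against.** A reader might infer that chance baseline differences will be taken for drug effects on sleep. The documents do not support that. The CSHQ starts at Visit 0 and is summarised at each visit by arm, so the Visit 0 means sit in the same table and an imbalance would be seen. No between-arm CSHQ test, confidence interval or decision rule is planned, and all CSHQ data are listed.

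Nor should the chance of an imbalance be read as the chance of a false finding. For one subscale, the probability that at least one of the four doses differs from placebo by 0.3 SD or more at Visit 0 is about 47% by simulation. That is the worst of four arms at baseline, before only a fraction r carries forward. For the pooled doses, a gap above 0.3 SD has a probability of 8.9%.

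Three further points have weight. Insomnia is also captured as an adverse event and tabulated by arm, severity and week of onset (SAP 11.1). The precision gain rests wholly on an assumed correlation. Table specifications are in a separate document (SAP 1), and change columns might appear there.

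These points limit the consequence but do not remove the gap. Seeing an imbalance does not adjust for it, a listing is not a summary, and the SAP text is where the analysis should be specified, as it is for the other measures.

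**Conclusion.** The point holds as a minor one. A baseline is defined and scheduled for the CSHQ, but no specified analysis measures change from it or adjusts for it, and the SAP gives no reason for treating it differently from laboratory values, vital signs, ECG and the sleep diary. What is lost is the within-child change with its SD, the restriction to children with both values, and a baseline-adjusted difference from placebo.

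The size is modest: a chance Visit 0 difference has an SE of 0.22 SD per dose and 0.18 SD pooled, of which about r carries into the raw follow-up difference. At an assumed r of 0.4 to 0.8, adjustment leaves 84% to 36% of the raw variance. These figures assume the planned 195 children, equal variances at both visits and a Visit 0 form for each child; the schedule asks for that form but cannot guarantee it.

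The primary and key secondary analyses, the sample size and type I error are unaffected. The wrong visit label is a separate error in the same section and stands regardless.

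**What to change.** In SAP 11.6, keep the current CSHQ sentence, because it carries the item-level summaries, the named statistics and the observed values at every visit including Visit 0. After it, add:

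*Change from baseline (Visit 0) in each subscale will be summarised by treatment group at each post-baseline visit in subjects with both values; for multi-item subscales the Visit 6 difference from placebo, adjusted for the Visit 0 score, will be given with 95% CI, descriptively and without multiplicity adjustment.*

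The limit to multi-item subscales leaves out sleep-onset delay, which is a single item. Replace Visit 8/ET with Visit 6/ET in both places.

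The cost is SAP wording and some extra table columns, with no new data. Seven multi-item subscales by four doses gives 28 unadjusted intervals, or 35 with the pooled doses, so they need the descriptive label. The adjusted Visit 6 difference still uses only children with a Visit 6 score and does not by itself deal with dropout.

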11.7 Columbia-Suicide Severity Rating Scale

Number of subjects and frequency with suicide-related events, based on the C-SSRS data, will be tabulated for the Safety Analysis Set for the following categories:

1. Wish to be dead
2. Non-specific active suicidal thoughts
3. Active suicidal ideation with any methods (not plan) without intent to act
4. Active suicidal ideation with some intent to act, without specific plan
5. Active suicidal ideation with specific plan and intent
6. Preparatory acts or behavior
7. Aborted suicide, attempt
8. Interrupted attempt
9. Actual attempt (non-fatal)
10. Completed suicide

11. Self-Injurious behavior without suicidal intent

A listing of the C-SSRS data will be provided for subjects with a positive response for the Safety Analysis Set.

11.8 Follow-up Phone Call

A listing will be created to show the date of the follow-up phone call.

12. CLINICAL PHARMACOKINETIC AND PHARMACODYNAMIC ANALYSES

Not applicable.

13. OTHER ANALYSES

See Section [10.5.2](#).

14. INTERIM ANALYSIS

See Sections [2.6](#) and [15](#).

15. DATA MONITORING/REVIEW COMMITTEE

An external independent Data Monitoring Committee (DMC) was set up to review the data pertaining to safety, tolerability, and benefit/harm of the study therapy for the duration of this Pediatric Written Request program, which includes studies SPD489-211, SPD489-347, and SPD489-348. The same DMC will evaluate the efficacy analysis results and supportive safety summaries to determine if the interim efficacy criteria are met for this study.

Confidentiality of the unblinded DMC analyses is a critical concern, and to address this, an unblinded independent reporting team will be identified within an external contract research organization. The independent reporting team will have no involvement in the conduct of the study. Further details regarding the DMC and the independent reporting team can be found in the DMC charter.

The DMC and the independent reporting team will not be involved in the blinded sample size re-estimation and dose-response relationship evaluations.

16. COMPUTER METHODS

Statistical analyses will be performed using Version 9.4 (or newer) of SAS® on a suitably qualified environment.

17. CHANGES TO ANALYSES SPECIFIED IN PROTOCOL

Not applicable.

18. DATA HANDLING CONVENTIONS

18.1 General Data Reporting Conventions

Continuous variables will be summarized using the following descriptive statistics: n, mean, median, SD, minimum, and maximum. The minimum and maximum values will be presented to the same number of decimal places as the raw data. The mean and median will be presented to one more decimal place than the raw data. The SD will be presented to 2 more decimal places than the raw data, whenever it is appropriate. Categorical and count variables will be summarized by the number of subjects (n) and the percent of subjects in each category. Percentages will be reported to 1 decimal place, except when the percentage equals exactly 100 where it will be displayed as an integer (100). For zero, only count and no percentage will be displayed.

18.2 Derived Efficacy Endpoints

18.2.1 Primary Efficacy Endpoint

The ADHD-RS-IV Preschool Version is an 18-item questionnaire that requires the respondent to rate the frequency of occurrence of ADHD symptoms as defined by Diagnostic and Statistical Manual of Mental Disorders Fourth Edition – Text Revision criteria. Each item is scored on a 4-point scale ranging from 0 (never or rarely) to 3 (very often) with total score ranging from 0 to 54. The 18 items may be grouped into 2 subscales: hyperactivity/impulsivity (even-numbered items 2-18) and inattentiveness (odd-numbered items 1-17).

A missing individual item in the ADHD-RS-IV Preschool Version will be imputed as follows:

- If only 1 single item is missing in a given subscale, the mean score for all other items in the subscale for the specific visit will be imputed as the score rounded up to the nearest integer for the missing score. The total score is computed as the sum of the imputed subscale scores.
- If more than 1 item is missing in a subscale, then the subscale score will be set to missing.
- Both subscales (hyperactivity/impulsivity and inattentiveness) must be non-missing in order to calculate the total score.

18.2.2 Key Secondary Endpoint

The key secondary efficacy endpoint, CGI-I, provides an overall assessment of global symptom improvement. For a supportive analysis, the CGI-I categories will be dichotomized into 2 categories: “very much improved” and “much improved” classified as “improved,” and all other assessed categories grouped together as “not improved.”

18.3 Repeated or Unscheduled Assessments of Safety Parameters

If a subject has repeated assessments before the start of investigational product, then the results from the final assessment made prior to the start of investigational product will be used as baseline. If end-of-study assessments are repeated or unscheduled, the last post-baseline assessment while on investigational product will be used for generating descriptive statistics. However, all post-baseline assessments will be used for PCI value determination and all assessments will be presented in the data listings.

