### **4.4 Discontinuation of Subjects**

A subject (parent[s]/LAR) may withdraw from the study at any time for any reason without prejudice to their future medical care by the physician or at the institution. The investigator or sponsor may withdraw the subject at any time for any reason (eg, in the interest of subject safety). The investigator is encouraged to discuss withdrawal of a subject from the clinical study with the medical monitor.

Upon discontinuation of the investigational product, regardless of the reason, the evaluations listed for Visit 6 are to be performed as completely as possible. Whenever possible, all discontinued subjects should also undergo the protocol-specified follow-up. Comments (spontaneous or elicited) or complaints made by the subject must be recorded in the source documents. The reason for termination and date of stopping investigational product must be recorded in the case report form (CRF) and source documents.

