10. EFFICACY ANALYSES

The primary and key secondary analyses, including their sensitivity analyses, will be based on the FAS and will be conducted on either the interim analysis dataset, which is defined in Section 2.6, or all cumulative data up to study completion, whenever it is appropriate. Specifically, these analyses will compare placebo and pooled SPD489 10, 20, 30 mg dose strengths together, excluding the 5 mg arm. For primary and key secondary endpoints, statistical tests are planned to control the study-wise type I error at the 2-sided 5% level, as described in Section 2.6. All other statistical tests will be 2-sided hypothesis tests performed at the 5% level of significance, with no adjustment for multiplicity. All confidence intervals (CIs) will be 2-sided 95% CIs, unless stated otherwise. Additionally, the dose response relationship evaluations will be performed over the DRAS and using appropriate datasets. For this analysis, all randomized investigational product groups, which include 0 (placebo), 5, 10, 20, 30 mg (SPD489) dose strengths will be used.

Baseline for all efficacy analyses is defined as the last valid value for the efficacy assessment prior to the first dose of investigational product. An efficacy measurement that is assessed more than 3 days after the date of the last dose of investigational product will not be included for analysis.

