11.1 Adverse Events

Adverse events will be coded using Version 18.0 or newer of the Medical Dictionary for Regulatory Activities.

An AE (classified by preferred term [PT]) that occurs during the Evaluation Period will be considered a TEAE if it has a start date on or after the first dose of investigational product or if it has a start date before the date of the first dose of investigational product, but increases in severity on or after the date of the first dose of investigational product. If more than 1 AE with the same PT is reported before the date of the first dose of investigational product, then the AE with the greatest severity will be used as the benchmark for comparison to the AEs occurring during the Evaluation Period under the preferred term. An AE that occurs more than 3 days after the date of the last dose of investigational product will not be counted as a TEAE.

An overall summary of number of subjects with TEAEs in each treatment group will be presented by treatment group, including the number and percentage of subjects with any TEAEs, serious TEAEs, TEAEs related to investigational product, TEAEs leading to withdrawal, severe TEAEs, and TEAEs leading to death.

Number and percentage of subjects reporting TEAEs in each treatment group will be tabulated by system organ class (SOC) and PT. TEAEs will be further summarized by maximum severity and relationship to investigational product. If more than 1 AE occurs with the same PT for the same subject, then the subject will be counted only once for that PT using the most severe and most related occurrence for the summarization by severity and by relationship to investigational product.

The incidence of TEAEs, serious TEAEs, and TEAEs leading to withdrawal will be summarized by SOC, PT, and treatment group, sorted in decreasing frequency for subjects on SPD489 then for placebo. The incidence of common ($\geq 2\%$ of subjects in any treatment group) will be summarized by PT and treatment group, sorted in decreasing frequency for subjects on SPD489 and then for placebo.

The number and percentage of subjects reporting TEAEs over the Safety Analysis Set will also be presented by week of AE onset, preferred term and treatment group, where week of AE onset is calculated as (AE occurred date – first dose date + 1) / 7, then rounded up to an integer.

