All information about AEs collected on the electronic case report form will be listed alongside the dose, PT, and SOC. For serious TEAEs, deaths, AEs related to the investigational product, and TEAEs leading to study discontinuation, a separate listing will also be provided.

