11.3 Vital Signs

Descriptive statistics (n, mean, SD, minimum, median, and maximum) for vital sign variables (systolic and diastolic blood pressure, pulse rate, body weight, temperature, and respiration rate), and their changes from baseline at each assessment time point will be presented by treatment group.

Body weight is collected at every visit, while height is collected only at Screening and the last scheduled visit/ET. At each visit excluding the last scheduled visit/ET, the Screening height will

be used to derive BMI values. For the last scheduled visit/ET, corresponding height and body weight will be used to calculate the BMI values. The resulting BMI values will be rounded to 1 decimal place for reporting. Descriptive statistics for BMI will be tabulated by visit and treatment group for actual values and change from baseline.

Percentiles of body weight and BMI can be normalized by sex and age using the CDC growth charts ([Kuczmarski et al. 2002](#)). Descriptive statistics of percentiles, for both, body weight, and BMI will be generated by visit and treatment group, for actual values and change from baseline.

Furthermore, the body weight percentiles can be categorized as <5th, 5th to <95th, and ≥95th percentiles, and the BMI percentiles can be categorized as: Underweight – BMI less than the 5th percentile; Healthy Weight – BMI 5th percentile up to less than the 85th percentile; Overweight – BMI 85th percentile to less than the 95th percentile; and Obese – BMI greater than or equal to the 95th percentile. Post-baseline shifts in body weight and BMI percentile category from baseline at each visit will be presented by treatment group. The data also will be presented categorically using number of subject and percentages at each visit by treatment group.

Additionally, figures with the mean change from baseline ± SD of the vital signs values (systolic and diastolic blood pressure, and pulse), weight, and BMI will be presented by treatment group and visit.

All vital sign values will be listed for the Safety Analysis Set.

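### SAP 18.3 limits safety summaries to on-product readings only in part and without a number of days, so a single late early-termination reading can enter the Visit 6/ET tables

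*SAP*

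**What the plan says.** Two parts of the SAP carry an explicit limit of 3 days after the last dose:

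- Efficacy (SAP 10): "An efficacy measurement that is assessed more than 3 days after the date of the last dose of investigational product will not be included".
- Adverse events (SAP 11.1): "An AE that occurs more than 3 days after the date of the last dose of investigational product will not be counted as a TEAE". Later events are not lost, because the same section adds: "All information about AEs collected on the electronic case report form will be listed alongside the dose, PT, and SOC".

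The descriptive safety summaries carry no such limit:

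- Vital signs and weight (SAP 11.3): the values and "their changes from baseline at each assessment time point will be presented by treatment group". BMI at the last visit or ET uses the height and weight taken there.
- ECG (SAP 11.4): "A shift table from baseline to each visit (and Visit 6/ET) for qualitative ECG results will also be presented".

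The only on-product condition for these parameters is in SAP 18.3: "If end-of-study assessments are repeated or unscheduled, the last post-baseline assessment while on investigational product will be used for generating descriptive statistics". That section also sends every post-baseline value to the PCI determination and every assessment to the listings.

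On the source of late readings, Protocol 4.4 says that after a child stops product "the evaluations listed for Visit 6 are to be performed as completely as possible". It states no maximum delay. Protocol 7.1.2.3 has all randomized children who stop early complete Visit 6/ET, and Protocol 4.4.3 asks children lost to follow-up to return for safety evaluations, again with no time limit.

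**The concern.** By cutting efficacy and TEAE data at 3 days, the SAP treats data collected later as no longer representing treatment. Blood pressure, pulse, weight and ECG are named in the safety objective (Protocol 2.2.2), yet a single ET reading of these is not clearly held to any limit. Such a reading may be taken after the drug effect has gone and still be summarised under the randomized dose.

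The expected signal is small. Protocol 1.2.2 puts the average stimulant effect at about 2-4 mmHg and 3-6 bpm, so a modest share of off-drug readings could visibly shrink the last-visit mean change. The SAP also leaves room for two readings. If an ET visit counts as unscheduled, 18.3 selects an earlier on-product value. If it does not, the ET value itself is used. Two programmers could then build different Visit 6/ET tables from the same data.

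**Working it through.** **Step 1. Does 18.3 cover a single ET assessment?** Its condition is that the end-of-study assessment was repeated or unscheduled. Visit 6/ET is a column of the Schedule of Assessments (Protocol Table 1) and is required of early stoppers (Protocol 7.1.2.3). Protocol 7.1 uses the word unscheduled for additional safety visits. On the natural reading, one ET assessment falls outside the rule. The opposite reading is possible, and 18.3 does not exclude it. Under either reading, the on-product condition has no number of days.

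**Step 2. How many ET visits does the plan expect?** Inputs are 156 completers and 20% dropout (SAP 2.5).

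- Randomized: 156 / (1 - 0.20) = 195, which matches the plan.
- Expected early terminations: 0.20 × 195 = 39.
- Allocation 5:5:5:5:6: each active arm 195 × 5/26 = 37.5, and placebo 195 × 6/26 = 45.
- Early terminations at a uniform 20%: 7.5 per active arm, 22.5 in the pooled 10, 20 and 30 mg arms (0.20 × 112.5), and 9 on placebo.

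**Step 3. How much could the last-visit mean shrink?** The inputs are the effects in Protocol 1.2.2 and the dropout in Step 2. Let f be the share of dropouts whose ET reading is fully off drug. Assume that the Visit 6/ET row combines completers and early terminators, that the effect has gone in the share f, and that all other readings carry the full effect. Then:

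observed mean change = on-drug mean change × (1 - 0.20 × f)

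| f (assumed) | Dilution | Blood pressure, 2-4 mmHg reads | Pulse, 3-6 bpm reads |
|---|---|---|---|
| 0 | 0% | 2.0-4.0 | 3.0-6.0 |
| 0.25 | 5% | 1.9-3.8 | 2.85-5.7 |
| 0.50 | 10% | 1.8-3.6 | 2.7-5.4 |
| 1.00 | 20% | 1.6-3.2 | 2.4-4.8 |

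The bottom row is the upper bound at the planned dropout: a loss of 0.4-0.8 mmHg and 0.6-1.2 bpm. It requires every dropout to return with the effect gone. The documents do not give the timing of ET visits, so f cannot be estimated from them.

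**Step 4. What is unaffected?** Blood pressure, pulse, weight and ECG are also measured at Visits 1-5 (Protocol Table 1) and summarised by time point. PCI counts use all post-baseline values. Only the Visit 6/ET part of the descriptive tables, shift tables and figures is exposed.

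**The case against.** The strongest reply is that 18.3 already contains an on-product rule. An ET visit does not fall on the planned Day 42, and the late recall of a child lost to follow-up is harder still to call scheduled, so both could be read as covered. This stands in part: the SAP does have a limit, but it is incomplete and undefined.

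The second reply concerns timing. Protocol 4.4 calls for the Visit 6 evaluations on discontinuation. Protocol 7.2 requires both the ET assessments and the follow-up call, and Protocol 7.1 puts that call 7 days (+3) after the last dose. The planned sequence therefore places ET before about Day 7-10 off drug. Where stopping is decided at a visit, the ET assessment can be done then, on drug. This makes a large f unlikely, but it does not bring ET inside 3 days.

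Third, dropouts may differ from completers. Protocol 4.4.2 lists meeting the blood pressure or pulse criteria as a reason for discontinuation, so the net effect on a combined mean is uncertain. This also stands, and it is why the dilution is called plausible and not shown.

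Finally, the safety analyses are descriptive, and no hypothesis test depends on these tables. That limits the consequence but does not make the last-visit summary well defined.

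**Conclusion.** The point holds as a gap in the on-product rule. As written, the SAP lets a single ET assessment made more than 3 days after the last dose enter the Visit 6/ET summaries of vital signs, weight, BMI and ECG. For pulse and blood pressure the plausible effect is a diluted last-visit mean change: at most 20% at the planned dropout, and 5-10% if a quarter to a half of dropouts are read off drug. These figures assume that the effect has fully gone in those children and that dropouts otherwise resemble completers.

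A reader might infer more: that the SAP sets no limit at all for these parameters, and that it therefore understates cardiovascular and weight effects and flattens the dose trend. The documents do not support this. Section 18.3 sets a partial limit. No off-drug time course is given for weight, BMI or QTc, so the direction there is unknown. No dropout rate by dose is given, so a distorted dose trend cannot be shown. On-drug changes remain visible at Visits 1-5 and in the PCI counts. Nor are late adverse events discarded: they are listed, though not counted as TEAEs.

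The matter should be corrected before unblinding. It does not affect the efficacy conclusion.

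**What to change.** In SAP 18.3, define on product as within 3 days of the last dose, the window the SAP already uses for efficacy and TEAEs. State that it applies to a single ET assessment as well as to repeated or unscheduled ones. In 11.3 and 11.4, apply it to the descriptive statistics, shift tables and change-from-baseline figures for vital signs, weight, BMI and ECG. Keep later readings in the listings and the PCI tabulation, flagged as off drug.

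The cost is a few lines of SAP text and one derived flag. The date of stopping product is already recorded (Protocol 4.4), and SAP 18.4 deals with a missing last-dose date. The downside is slightly fewer readings in the Visit 6/ET summaries.
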